8.8.3 Patient-Reported Outcomes

The EQ-5D-5L qualitative items will be presented as the number and % of patients with each rating of health for each quality of life category (such as mobility), summarised over all

scheduled visits. The number and % of patients with each shift item from baseline to EOT and from baseline to EOS will also be summarized.

The EQ-5D-5L qualitative items will be presented by means of a stacked bar chart over all applicable scheduled visits.

Descriptive statistics will be summarized for the visual analogue scale score.

8.9 Safety

Frequency tables will be used to present the safety outcomes including incidences of TEAEs, SAEs (including deaths), TEAEs leading to death, treatment-emergent AESIs, liver-related TEAEs, TEAEs leading to premature treatment discontinuation, TEAEs leading to premature study withdrawal, TEAEs by relationship and TEAEs by severity.

Change from baseline and incidence of pre-defined treatment-emergent newly occurring abnormalities in vital signs, clinical laboratory test results and ECG results will be summarised. Graphical presentations will also be used to help describe vital signs, selected laboratory test values and ECG parameters.

Other safety outcomes include physical examination [REDACTED]

Safety data collected for the main study phase up to Day 84/Day 90 and the subsequent 4-week FU visit will be included in the data analyses and presented in the CSR. Safety data collected during ET and ET FU will not be included in the data analyses or in the CSR, and will be presented in the report addendum.

8.9.1 Exposure

Overall exposure will be summarised by taking individual dose modification and dose intensity into account.

8.9.2 Adverse Events

Adverse events will be coded using MedDRA. Number of events and incidence rates will be tabulated by System Organ Class and Preferred Term. An event that occurs at least once on the date of, or subsequent to first administration of study drug will contribute one observation to the numerator of the incidence rate. The denominator of the rate will comprise all patients exposed to the study drug (SAF analysis set). If the intensity or seriousness of the AE changes, the overall severity or seriousness will be the worst severity or seriousness of the multiple occurrences.

TEAEs, SAEs (including deaths), TEAEs leading to death, treatment-emergent AESIs, liver-related TEAEs, TEAEs leading to premature treatment discontinuation and TEAEs leading to premature study withdrawal will be tabulated. In addition, TEAEs by relationship and severity (using CTCAE grading) will be summarised.

8.9.3 Clinical Laboratory Evaluations

All central laboratory test results will be summarised using descriptive statistics at each visit for observed data and change from baseline.

Based on the laboratory reference range, laboratory test results will be categorised as:

- Low
- Normal
- High

Change from baseline to each post-baseline visit, main study phase EOT and EOS in aforementioned reference range laboratory category will be presented as shift tables. Abnormal laboratory values, categorised per reference range as high or low will be flagged in by-patient data listings.

In addition, pre-defined treatment-emergent abnormalities (newly occurring), as defined by CTCAE criteria, will be presented in tables where the incidence rate will be based on the total number of patients 'at risk':

For example:

- If a CTCAE criterion involves a change from baseline, evaluable patients would have both a pre-dose and at least 1 post-dose value recorded
- If a CTCAE criterion does not consider changes from baseline, to be evaluable the patient need only have 1 post-dose value recorded.

In the event that a laboratory value does not comply with the CTCAE criterion, the laboratory value will be categorised as normal.

In the event of a retest of the same sample due to, for example, a laboratory error (same visit number assigned), the last available assessment will be used for by-visit summaries, including identification of pre-defined treatment-emergent abnormalities (newly occurring), regardless of whether the laboratory assessment for that particular nominal visit is available or not.

The handling of laboratory values below limit of quantification (LOQ) will be described in the detailed SAP for each laboratory test separately.

It should be noted that for glucose, only non-fasting values will be included in any summary presentations although all results will be listed in by-patient listings.

As per the FDA Liver Safety Guidance, the following treatment-emergent incidence tables will be presented, including time-to-event analyses, and by-patient data listings:

- $3 \times$ -, $5 \times$ -, $10 \times$ -, and $20 \times$ ULN elevations of AST, ALT, and either ALT or AST.
- Any elevations of total bilirubin, elevated total bilirubin $> 2 \times$ ULN.
- Any elevations of alkaline phosphatase (ALP) $> 1.5 \times$ ULN.

- Elevation of AST or ALT $> 3 \times$ ULN accompanied by elevated total bilirubin ($> 1.5 \times$ ULN, $> 2 \times$ ULN).
- Elevation of AST or ALT $> 3 \times$ ULN in temporal association with nausea, vomiting, anorexia, abdominal pain, or fatigue.

Treatment-emergent is defined as any event (scheduled or unscheduled) which started or worsened on or after the first dose of study drug or during the post-treatment FU. Treatment-emergent AEs which occur in the main study phase or FU will be presented in the study report; TEAEs which occur in the ET phase or post-ET FU will be presented in the report addendum.

In addition, figures and listings will be presented for possible treatment-emergent Hy's Law cases (patients with any elevated AST or ALT $> 3 \times$ ULN, ALP $< 2 \times$ ULN and associated with an increase in total bilirubin $\geq 2 \times$ ULN).

[REDACTED]

[REDACTED]

[REDACTED]

8.9.4 Vital Signs Measurements, ECG, Physical Findings and Other Safety Evaluations

8.9.4.1 Vital Signs

Vital signs (systolic blood pressure, diastolic blood pressure, pulse rate, respiratory rate, body temperature, weight and BMI) will be summarised using descriptive statistics at each visit for observed data and change from baseline.

Pre-defined treatment-emergent abnormalities (newly occurring), as defined by CTCAE criteria, will be presented in tables and listed, where the incidence rate will be based on the total number of patients 'at risk' (see example in Section 8.9.3).

A similar approach as for laboratory values will be followed for vital signs with regards to retests and values not complying with CTCAE criterion.

8.9.4.2 ECG

ECG results will be summarised using descriptive statistics at each visit for observed data and change from baseline.

Pre-defined QT interval treatment-emergent abnormalities, as defined by CTCAE criteria, will be presented in tables and listed, where the incidence rate will be based on the total number of patients 'at risk' (see example in Section 8.9.3).

A similar approach as for laboratory values will be followed for ECG with regards to retests and values not complying with CTCAE criterion.

Change from baseline to each post-baseline visit, main study phase EOT and EOS in Investigator-judged abnormal classification will be presented as shift tables:

- Abnormal and clinically significant
- Abnormal and not clinically significant
- Normal.

8.9.4.3 Other Safety Evaluations

Any abnormal physical examination findings, as judged by the Investigator, will be listed in a by-patient data listing only.

Any abnormal physical examination findings, as judged by the Investigator, will be listed in a by-patient data listing only.

8.10 Hospitalisation Status

The reason, date of admission and discharge, type of ward (intensive care unit, non-intensive care unit) and any changes in any of these parameters recorded in the eCRF will be summarised descriptively (sample size [n], absolute and relative frequencies [n and %]).

8.11 Pharmacokinetic Analyses

Blood samples for analysis of plasma concentrations of study drug will be collected as specified in the Schedule of Events (Table 1).

All PK sample collections and concentrations will be listed and summarised by visit. Pharmacokinetic data collected for the main study phase up to Day 84/Day 90 and the subsequent 4-week FU visit will be included in the data analyses and presented in the CSR. Pharmacokinetic data collected during ET and ET FU will not be included in the data analyses or in the CSR, and will be presented in the report addendum.

8.11.1 Trough Sampling Data Analysis

All drug concentrations will be listed and presented in tabular summaries using descriptive statistics, including n, arithmetic mean, standard deviation, coefficient of variation, median, geometric mean, geometric coefficient of variation, minimum and maximum values.

The trough concentrations and post-dose concentrations will be used for a population PK analysis of F901318. The population PK of F901318 will be characterised by nonlinear mixed-effects modelling. From this analysis, the influence of various demographic covariates (e.g., body weight, gender) and other patient-specific factors on F901318 trough levels and drug exposure may be assessed. Correlations between exposure and response or safety data will be evaluated as appropriate.

The data from this study may be combined with data collected from other studies and from the Intensive PK component of this study to supplement model development. The population PK analysis will be performed in accordance with a separate modelling data analysis plan and may be reported outside of the CSR.

8.11.2 Intensive PK Data Analysis

The Intensive PK study will include densely sampled PK to allow parameters to be determined using standard noncompartmental analysis. All PK parameters where possible to estimate will be listed and summarised using appropriate descriptive statistics including maximum plasma concentration (C_{max}), time to maximum plasma concentration (t_{max}), area under the curve over the 12 hour dosing interval (AUC_{tau}), trough concentration 12 hours post-dose (C_{min}), apparent clearance (CL/F) and apparent volume of distribution (V_z/F). Data will be listed and summarised using n, arithmetic mean, standard deviation, coefficient of variation, median, minimum and maximum values. Geometric mean and geometric coefficient of variation will also be included for any PK parameter calculations, except for t_{max} which will be summarised using n, minimum, median and maximum only. Full details of the analysis will be provided in the SAP supporting this clinical study.

8.12

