17. PHARMACOKINETIC ANALYSIS

[figure not shown]
The PK parameter calculations will be the responsibility of the clinical pharmacokineticist at IQVIA, Overland Park, Kansas, United States. The concentration summaries, PK parameter summaries, data listings, and associated graphic presentation will be the responsibility of the study biostatistician at IQVIA, Bloemfontein, South Africa.

Scheduled intensive PK day plasma concentrations and PK parameters for olorofim (central bioanalytical lab) will be summarized using descriptive statistics, including n, mean, SD, coefficient of variation (CV%), median, minimum, and maximum. geometric mean, and CV% for geometric mean (GeoCV%). For time of maximum concentration (Tmax), only n, median, minimum, and maximum will be provided. If the number of non-missing observations at a time point is fewer than 3, the data at the time point will not be summarized. Scheduled intensive PK day plasma concentrations and PK parameters will be summarised by dosing methodology (adjusted (all), adjusted (BID), adjusted (TID) or fixed dosing) using descriptive statistics, including n, mean, median, 95% CI, minimum and maximum. Intensive PK day PK parameters will also be summarised by concomitant medication (CYP3A4 inhibitors and inducers) demographics (age, sex, race) and underlying condition (immune status, baseline creatinine clearance, GvHD) using descriptive statistics, including n, mean, median, 95% CI, minimum, and maximum.

In general, scheduled trough data (central bioanalytical lab and regional hub) will be summarised by dosing methodology (adjusted or fixed dosing) and regimen (BID or TID) using descriptive statistics, including including , mean, SD, coefficient of variation (CV%), median, minimum, and maximum, geometric mean, and CV% for geometric mean (GeoCV%). Trough parameters will be summarised by dosing methodology (adjusted (all), adjusted (BID), adjusted (TID) or fixed dosing), concomitant medication (CYP3A4 inhibitors and inducers), demographics (age, sex, race) and underlying condition (immune status, baseline creatinine clearance, GvHD) using descriptive statistics, including n, mean, median, 95% CI, minimum, and maximum.

Document: \\weedc-vnasc01\BIOSdata\F2G\F901318 [REDACTED]
Author: [REDACTED] Version Number: 3.0
Version Date: 06Apr2023
Template No.: CS_TP_BS016 Revision 6 Reference: CS_WI_BS005
Effective Date: 02Dec2019

F2G Ltd.
PROTOCOL F901318/0032

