17.1.1. CONCOMITANT MEDICATIONS

Document: \\weedc-vnasc01\BIOSdata\F2G\F901318 [REDACTED]
Author: [REDACTED] Version Number: 3.0
Version Date: 06Apr2023
Template No.: CS_TP_BS016 Revision 6 Reference: CS_WI_BS005
Effective Date: 02Dec2019

F2G Ltd.
PROTOCOL F901318/0032

Selected olorofim trough parameters will be summarized by concomitant medication group (no/weak inhibitors of CYP2C9 and CYP3A4, moderate inhibitors of CYP2C9 or CYP3A4, strong inhibitors of CYP2C9 or CYP3A4, dual moderate inhibitors of CYP2C9 and CYP3A4, no/weak inducers of CYP3A4, moderate or strong inducers of CYP3A4) provided the medication has been administered to at least three subjects during the main phase of the study. Individual data will be listed for all cases where these concomitant medications are administered during the main phase of the study.

Selected olorofim PK parameters will be summarized by concomitant medication group (no/weak inhibitors of CYP2C9 and CYP3A4, moderate inhibitors of CYP2C9 or CYP3A4, strong inhibitors of CYP2C9 or CYP3A4, dual moderate inhibitors of CYP2C9 and CYP3A4, no/weak inducers of CYP3A4, moderate or strong inducers of CYP3A4) provided the medication has been administered to at least three subjects on the intensive PK day. Figures of mean and 95% confidence interval will also be presented graphically for each concomitant medication group. Individual data will be listed for all cases where these concomitant medications are administered on the intensive PK day.

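### Subgroup PK tables and figures list the mean and 95% CI without the geometric mean and geometric CV that Protocol 8.11.2 requires for PK parameters, and the CI formula is not stated

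*Protocol*

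**What the plan says.** Protocol 8.11.2 lists arithmetic statistics for the intensive PK parameters and then adds: "Geometric mean and geometric coefficient of variation will also be included for any PK parameter calculations". Only tmax is exempt. For drug concentrations, Protocol 8.11.1 asks for "arithmetic mean, standard deviation, coefficient of variation, median, geometric mean, geometric coefficient of variation, minimum and maximum values".

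SAP 17 follows this in two places: the overall summary of the intensive PK day, and the scheduled trough concentrations by dosing methodology and regimen. Both include the geometric mean and GeoCV%.

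Elsewhere in SAP 17 the list is shorter:

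- Intensive-day data by dosing methodology are summarised "using descriptive statistics, including n, mean, median, 95% CI, minimum and maximum".
- Next comes: "Intensive PK day PK parameters will also be summarised by concomitant medication (CYP3A4 inhibitors and inducers) demographics (age, sex, race) and underlying condition". That sentence ends "GvHD) using descriptive statistics, including n, mean, median, 95% CI, minimum, and maximum".
- Trough parameters by dosing methodology, co-medication, demographics and underlying condition get the same short list.

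For figures, SAP 17.1.1 says: "Figures of mean and 95% confidence interval will also be presented graphically for each concomitant medication group". SAP 17.1 and 17.2 plan the same display for the demographic and underlying-condition subgroups. A co-medication group is summarised "provided the medication has been administered to at least three subjects on the intensive PK day". Trough parameters by co-medication have a matching three-subject rule. No minimum is stated for the patient subgroups.

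SAP 6.6 fixes the confidence level at 95% and tests as two-sided, but gives no interval formula or scale for PK. No visible item in SAP 3.3 declares a change to the PK statistics; the one PK item there concerns the definition of the Intensive PK set.

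**The concern.** SAP 17 names the geometric mean separately wherever it wants it, so the plain mean in the short lists is the arithmetic mean. Exposure measures such as Cmax and AUC are positive and usually right-skewed. On such data an interval symmetric about the arithmetic mean can reach below zero, and when it misses it tends to lie too low.

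The affected outputs are the comparative ones, where a reader looks to see whether exposure differs by CYP inhibitor or inducer, dosing methodology, renal function or immune status. They bear on the secondary PK objective and the exploratory drug-interaction objectives. The protocol itself describes an interaction as a multiple: Section 2.1.3 reports 2.0-fold (AUC) and 1.7-fold (Cmax) increases with fluconazole. Multiples are most naturally read on the log scale.

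**Working it through.** **Figure to reproduce.** None. The documents give no CV, sample size or CI formula for these summaries.

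**Inputs.** Minimum co-medication group n=3 (SAP 17.1.1); 95% level (SAP 6.6). Assumed: log-normal data with a between-patient CV from 20% to 100%; a t interval, with a normal (z) interval as the alternative.

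**Step 1: when the lower limit is negative.** The arithmetic t interval is mean ± t(0.975, n−1) × SD/√n. Its lower limit is below zero when the sample CV exceeds √n / t(0.975, n−1).

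- n=3: 1.732 / 4.303 = 40.3%
- n=4: 2 / 3.182 = 62.8% (about 63%)
- n=5: 2.236 / 2.776 = 80.5% (about 81%)
- n=10: 3.162 / 2.262 = 139.8%

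With z instead of t, the n=3 threshold is 1.732 / 1.960 = 88.4%.

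**Step 2: how often that happens, and coverage.** Simulation of log-normal samples, 300,000 per cell. Coverage is of the true arithmetic mean.

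| Assumed CV | P(lower limit < 0), n=3, t | P(lower limit < 0), n=5, t | t coverage, n=3 | t coverage, n=5 | t coverage, n=10 | z coverage, n=3 |
|---|---|---|---|---|---|---|
| 20% | 1.5% | 0.0% | 94.7% | 94.4% | 94.6% | 80.6% |
| 30% | 13.7% | 0.0% | 94.1% | 93.8% | 93.9% | 79.9% |
| 50% | 45.7% | 2.6% | 92.6% | 92.0% | 92.3% | 77.7% |
| 70% | 64.3% | 13.7% | 90.7% | 89.7% | 90.5% | 75.2% |
| 100% | 77.5% | 34.4% | 87.3% | 85.8% | 87.2% | 71.3% |

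Across each row, t coverage hardly changes between n=3 and n=10. The loss is therefore due to skewness. Small n drives the width and the negative limits. Misses are lopsided: at CV 50% and n=3, 6.5% of intervals lie wholly below the true mean and 0.9% wholly above it.

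**Step 3: the log-scale interval.** Take the t interval of the logs and back-transform. Its target is the geometric mean. Simulated coverage was 94.8% to 95.2% at every n and CV tried, and the limits cannot be negative. With σ = √ln(1+CV²), the limits are about the geometric mean divided and multiplied by exp(t × σ/√n).

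- n=3: factor 2.07 at CV 30%, 3.23 at CV 50%, 7.91 at CV 100%
- n=10: 1.23, 1.40 and 1.81

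Example for n=3, CV 30%: σ = √ln(1.09) = 0.294, and exp(4.303 × 0.294 / 1.732) = 2.07.

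**The case against.** The strongest reply is that nothing required has been lost. Protocol 8.11 plans no subgroup tables. The overall intensive PK summary in SAP 17 does carry the geometric statistics, and the subgroup tables are additions. The short lists are introduced by the word *including*, so they need not be exhaustive. SAP 17.2 summarises parameters by dosing type with unspecified descriptive statistics, and the table templates mentioned in SAP 8 are not in the public documents. The outputs are descriptive, show median and range, and SAP 17.1.1 lists individual values for every co-medication case.

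Much of this stands, and it limits the point. A reader might infer that the SAP has abandoned geometric statistics; it has not. But neighbouring sentences also say *including* and do name the geometric mean and GeoCV%, so the omission reads as a different list. The subgroup figures are specified outright as mean with 95% CI.

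Other stronger readings also fail:

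- **The intervals are known to under-cover.** Neither the CV nor the formula is stated. With a t interval at CV 20-30% the loss is about one point or less. It is severe only with a z interval in very small groups.
- **Groups of 3 cause the under-coverage.** Coverage is much the same at n=10.
- **Patient subgroups may be as small as 3.** The rule covers co-medication only; for the others no minimum is given.
- **These tables are the sole evidence on interactions.** Protocol 8.11.1 also plans population PK modelling of patient-specific factors, under a separate plan.
- **The fluconazole multiples are geometric mean ratios.** Protocol 2.1.3 speaks only of the mean.

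Whether Protocol 8.11 reaches the trough parameters is a matter of reading. SAP 17 does treat the average trough as a PK parameter when setting rounding rules.

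**Conclusion.** The point holds as a mismatch between protocol and SAP, limited to the subgroup summaries and figures. For intensive PK parameters by dosing methodology, co-medication, demographics and underlying condition, the SAP lists the mean and a 95% CI with no stated formula and leaves out statistics that Protocol 8.11.2 asks for. SAP 3.3 does not visibly declare the change.

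The negative-limit threshold (40% sample CV at n=3) is exact algebra for a t interval. The coverage figures of about 94%, 92-93% and 86-87% at CV 30%, 50% and 100% rest on an assumed log-normal distribution and assumed CVs. The primary endpoint is untouched. This is a free improvement to secondary and exploratory descriptive outputs.

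**What to change.** In SAP 17, 17.1, 17.1.1, 17.1.2 and 17.2:

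1. Keep the arithmetic statistics, since Protocol 8.11.2 requires the arithmetic mean as well. Add the geometric mean, GeoCV% and a 95% CI computed on the log scale and back-transformed. For tmax give n, median, minimum and maximum only.
2. Use the geometric mean and its CI in the subgroup figures.
3. State the CI formula.
4. Record any remaining departure from Protocol 8.11.2 in SAP 3.3.
5. If co-medication contrasts are shown as geometric mean ratios, base them on the dose-normalised parameters already defined in SAP 17.2 and label them descriptive. Protocol 2.1.3 says the dose is reduced with moderate or strong CYP3A4 or 2C9 inhibitors, so ratios of unnormalised exposure would understate the interaction.

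The cost is SAP wording and a log transform in programs already planned, with no new data. The change corrects scale and coverage but does not make groups of 3 informative. At CV 30% the log-scale limits already span a factor of 2.07 either side, wider than the 2.0-fold fluconazole effect.

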8.13 Interim Analyses

An analysis of the data will be conducted when the first 100 patients have completed the main study phase.

Independent Data and Safety Monitoring Board (IDSMB)

See Section 6.4.4.1 for details.

Data Review Committee (DRC)

A DRC will be established to conduct a review of all patient cases to determine diagnosis and overall outcome. Members of the DRC will be independent from the Sponsor and also will not participate as Investigators in the study. The DRC will consist of experts in the field of clinical mycology.

The DRC assessment will include the clinical diagnosis at enrolment as well as primary and secondary criteria for efficacy evaluation. The DRC will not review data from the ET visits or the post-ET FU. Objectives, composition, process and documentation of the DRC are described in more detail in the DRC Charter and SAP.

